### **5.1.2 Safety Data**

The following safety data will be collected and evaluated according to the Study Calendar (Section 3.6):

- Clinical laboratory variables: serum biochemistry and hematology
- Injection site monitoring
- Pre-administration events (baseline signs and symptoms)
- AEs

SAEs will be recorded if they occurred as follows:

- After a subject first received Eovist® and throughout the subjects follow-up period,
- During the subject's follow up period, and for which a causal relationship to Eovist® cannot be ruled out.

Interpretation and follow-up of abnormal results will be done on a case by case basis in conjunction with the individual clinical situation. Any clinically significant abnormal finding, or change in one that represents a worsening from baseline, is an AE. Once a decision is reached to report a finding as an AE, the investigator is required to follow the procedure described for AE notification.

### **5.1.3 Imaging Data**

Extracted imaging data include:

- (1) All image data will be stored on a secure server, with access limited to credentialed users. This will permit flexible numeric raw data extraction for quantitative analysis and creation of summary data reports.
- (2) Anonymized image data from this study will be stored in a secure database that it is administered by the Cancer Imaging Program, NCI. The database is password protected and access is only given to qualifying collaborators.

## **5.2 Toxicity Criteria**

The following adverse event management guidelines are intended to ensure the safety of each patient while on the study. The descriptions and grading scales found in the revised NCI Common Terminology Criteria for Adverse Events (CTCAE) version 4.0 will be utilized for AE reporting. All appropriate treatment areas should have access to a copy of the CTCAE version 4.0. A copy of the CTCAE version 4.0 can be downloaded from the CTEP web site ([http://ctep.cancer.gov/protocolDevelopment/electronic\\_applications/ctc.htm#ctc\\_40](http://ctep.cancer.gov/protocolDevelopment/electronic_applications/ctc.htm#ctc_40)).

## **6 BIOSPECIMEN COLLECTION**

### **6.1 Tissue Samples**

All tissue specimens (slide specimens) should be obtained as specified in the protocol and will be barcoded and labeled as described in the following sections. Tissue samples will be stained for immunohistochemistry analysis of OATP1B3 expression in NIH (please see section [3.5.3](#)).

In patients with localized disease, tissue can be obtained from image guided biopsies or from prostatectomy specimens.

In patients with advanced disease, tissue will be obtained from a target lesion (measuring  $\geq 1.5\text{cm}$  in diameter at CT or MRI scan) by biopsy either incidental to this study or obtained specifically for this study.

### **6.2 Blood Samples**

Blood samples will be collected for screening and on-study clinical laboratory safety assessments. All blood samples will be processed and handled in accordance with standard laboratory procedures. All samples except for the one obtained for OATP1B3 genotyping will be analyzed at the NCI Clinical Center laboratory. The peripheral blood sample obtained for OATP1B3 genotyping will be analyzed in [name] Lab. Peripheral blood for DNA extraction will be collected in a 10-ml K2EDTA vacutainer. The vacutainer will be placed on wet ice after draw store in a  $4^{\circ}\text{C}$  refrigerator until pick-up. The research nurse ([name]) will record the date and time of draw on the blood tube label.

Please immediately page [name] for pick-up. Contact the Clinical Pharmacology Program (CPP) processing group in 10/5A09 at [contact] or [contact] with any questions.

### **6.3 Pathology Specimens**

#### **6.3.1 Surgical Pathology**

Specimens will be obtained from biopsy as described in Section [3.1.2](#) and mounted on glass slides. Slides will be labeled with study number, subject number, sampling date. Slide specimens will be stained to assess tumor tissue will be performed by one pathologist. IHC analysis will be conducted on slides to assess the expression of OATP1B3 (please see section [3.5.3](#)).

## **6.4 Sample Storage, Tracking and Disposition**

### **6.4.1 Sample Processing and Storage:**

Each patient research tissue sample will be assigned a unique patient identifier and relevant sample characteristics (such as timing of sample collection, treatment cycle and day identifiers) will be recorded. The location of all tissue samples will be carefully tracked in the secure database. All stored tissue samples will be coded and no identifying patient information will be placed on sample containers. Stored tissue samples will be kept in freezers / refrigerators or secure containers located in the NCI research laboratories or in the laboratories of collaborators.

For the blood samples obtained for genotyping, peripheral blood samples sent to the Clinical Pharmacology Program (CPP) will be barcoded, with data entered and stored in the Patient

Sample Data Management System (PSDMS) utilized by the CPP. This is a secure program, with access to PSDMS limited to defined CPP personnel, who are issued individual user accounts. Installation of PSDMS is limited to computers specified by [name]. These computers all have a password restricted login screen. All CPP personnel with access to patient information annually complete the NIH online Protection of Human Subjects course.

PSDMS creates a unique barcode ID for every sample and sample box, which cannot be traced back to patients without PSDMS access. The data recorded for each sample includes the patient ID, name, trial name/protocol number, time drawn, cycle time point, dose, material type, as well as box and freezer location. Patient demographics associated with the clinical center patient number are provided in the system. For each sample, there are notes associated with the processing method (delay in sample processing, storage conditions on the ward, etc.).

Barcoded samples are stored in barcoded boxes in a locked freezer at either -20 or -80°C according to stability requirements. These freezers are located onsite in the CPP and offsite at NCI Frederick Central Repository Services (Fisher Bioservices) in Frederick, MD. Visitors to the laboratory are required to be accompanied by laboratory staff at all times.

Access to stored clinical samples is restricted. Samples will be stored until requested by a researcher named on the protocol. All requests are monitored and tracked in PSDMS. All researchers are required to sign a form stating that the samples are only to be used for research purposes associated with this trial (as per the IRB approved protocol) and that any unused samples must be returned to the CPP. It is the responsibility of the NCI Principal Investigator to ensure that the samples requested are being used in a manner consistent with IRB approval.

Following completion of this study, samples will remain in storage as detailed above. Access to these samples will only be granted following IRB approval of an additional protocol, granting the rights to use the material.

If, at any time, a patient withdraws from the study and does not wish for their existing samples to be utilized, the individual must provide a written request. Following receipt of this request, the samples will be destroyed (or returned to the patient, if so requested), and reported as such to the IRB. Any samples lost (in transit or by a researcher) or destroyed due to unknown sample integrity (i.e. broken freezer allows for extensive sample thawing, etc.) will be reported as such to the IRB.

Sample barcodes are linked to patient demographics and limited clinical information. This information will only be provided to investigators listed on this protocol, via registered use of the PSDMS. It is critical that the sample remains linked to patient information such as race, age, dates of diagnosis and death, and histological information about the tumor, in order to correlate genotype with these variables.

#### **6.4.2 Timeframe for research studies**

Samples will be stored until requested by an authorized researcher(s). All researchers are required to use the samples for research purposes associated with this trial (as per the NCI IRB approved protocol). Subjects will be given the option of consenting to future use of their research samples per the informed consent process with their option declared in the consent document. Samples from those patients who consent to this will be stored permanently. However, these samples will be used only for research studies on active NCI IRB approved protocols covered by a valid informed consent document. Samples will be destroyed at the

completion of the study from those subjects who decline future use of their samples. Once primary research objectives for the protocol are achieved, intramural researchers can request access to remaining samples provided they have an IRB approved protocol and patient consent. Any unused samples must be returned to the NCI laboratories as appropriate. The PI will report destroyed samples to the IRB if samples become unsalvageable because of environmental factors (e.g. broken freezer or lack of dry ice in a shipping container) or if samples are destroyed because a patient withdraws consent. Samples will also be reported as lost if they are lost in transit between facilities or misplaced by a researcher. Any freezer problems, lost samples or other problems associated with samples will be reported to the IRB, the NCI Clinical Director, and the office of the CCR, NCI.

## **7 STATISTICAL CONSIDERATIONS**

### **7.1 Study Populations**

25 evaluable patients will be included in this trial with an accrual rate of 1-2 patients a month. Therefore, it is expected that this study enrollment will be completed within 1.5 years and full study goals within 2.5 years. We plan to enroll 25 evaluable patients (10 in arm 1 and 15 in arm 2).

### **7.2 Subject Characteristics**

Subject characteristics will be summarized with the following information:

- Number of subjects enrolled
- Number of subjects included in the safety analysis
- Number of subjects included in the efficacy analysis
- Number of subjects withdrawn from the study and the reason for withdrawal

Demographic information (age, height, weight, and body mass index) will be summarized using descriptive statistics. Race will be summarized by counts and percents.

Medical histories will be summarized by counts and percents. Concurrent medications will be recorded, coded and grouped by primary and secondary classes, if applicable.

### **7.3 Efficacy Analysis**

#### **7.3.1 Primary Efficacy Analysis**

The primary objective of the study is to evaluate the uptake and retention of Eovist® in prostate cancers measured by the change of MRI parameter values between pre- and post-injection (section 3.5.1). Log-transformed MRI parameter values between pre- and post-injection will be compared by the paired t-test. If the distribution of log-transformed MRI parameter values is skewed, nonparametric paired Wilcoxon signed-rank test will be used for comparison.

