## 1 INTRODUCTION

### 1.1 Study Objectives

#### 1.1.1 Primary Objective

- Evaluate the uptake and retention of Eovist® in prostate cancers

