#### 1.2.4 Rationale

No currently used imaging method evaluates the status of the OATP1B3 transporter. Such a method might be important in stratifying risk factors in patients, both with localized and with metastatic disease.

Eovist® (gadoxetate disodium) is a gadolinium-based contrast agent which was approved by the FDA in 2008 [6]. It is indicated for intravenous use in T1-weighted magnetic resonance imaging (MRI) of the liver to detect and characterize lesions in adults with known or suspected focal liver disease, particularly in the diagnosis of hepatocellular carcinoma (HCC). The agent

is taken up by normal hepatocytes and lesions that contain normal hepatocytes (e.g. focal nodular hyperplasia). The majority of HCCs do not take up Eovist® and so the agent has become useful in the workup of suspected HCC. However, some HCC tumors do take up Eovist® and this uptake has been correlated with their OATP1B3 expression [7, 8].

The agent is injected intravenously. Because it is a low molecular weight imaging agent it rapidly enhances all vascular organs and structures. However, it was not retained by non OATP1B3 expressing tissue and so at 20 minutes a correlation was made between OATP1B3 expressing lesions (persistent enhancement) and non OATP1B3 expressing lesions (washout of enhancement).

Thus, Eovist® will be used in patients with localized and metastatic prostate cancer in order to determine if this method is feasible to observe differences in uptake times in prostate cancers and whether these differences correlate with OATP1B3 expression in prostate cancer and therefore, might serve as a predictive biomarker.

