##### 3.1.1 Eovist® enhanced MRI

MRI will be performed in the Molecular Imaging Clinic. Pre contrast T1, T2 weighted scans with or without endorectal coil will be obtained through the prostate gland, bone metastasis or soft tissue metastasis (usually a lymph node) selected as the target lesion. Then 0.1 ml/kg Eovist® will be administered IV. Scans will be obtained immediately, 10, 20 and 60 minutes after injection using the same settings. Contrast enhancement ratios will be determined at each time point (Section 3.3).

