### **3.5 Correlative Studies**

#### **3.5.1 Imaging Correlation**

A volume of interest (VOI) will be drawn over the target lesion in the baseline and in post-Eovist® injection MR images and the amount of contrast enhancement will be recorded by using dedicated image analysis software (MIM 5.4 Software, MIM Software Inc. Cleveland, OH, USA). Enhancement ratios [(signal enhancement after enhancement-signal enhancement before enhancement)/signal intensity before enhancement] will be calculated on pre and post-injection T1W MR images.

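### The primary pre/post test names none of the four post-injection scans, no early-to-late contrast and no multiplicity rule, so the retention half of the primary objective has no defined analysis

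*Combined protocol and SAP*

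**What the plan says.** Section 1.1.1 gives the primary objective: "Evaluate the uptake and retention of Eovist® in prostate cancers". Section 7.3.1 says this is "measured by the change of MRI parameter values between pre- and post-injection" and refers to section 3.5.1. The test is then given as "Log-transformed MRI parameter values between pre- and post-injection will be compared by the paired t-test", with the Wilcoxon signed-rank test if the log values are skewed.

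On the scans, section 3.1.1 states: "Scans will be obtained immediately, 10, 20 and 60 minutes after injection using the same settings". The study calendar (3.6) and section 3.6.1.3 list the same four times. Section 3.1.1 adds: "Contrast enhancement ratios will be determined at each time point". Section 3.5.1 defines the enhancement ratio as the change in signal over the pre-injection signal and says that it "will be calculated on pre and post-injection T1W MR images", without naming a scan. Section 7.4 averages multiple lesions within a subject and bases the paired t-test on log signal values, but does not mention multiple time points.

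The rationale (1.2.4) is specific about timing. Of early enhancement it says: "Because it is a low molecular weight imaging agent it rapidly enhances all vascular organs and structures". Of later behaviour it says that "it was not retained by non OATP1B3 expressing tissue and so at 20 minutes a correlation was made" between expressing lesions, which kept their enhancement, and non-expressing lesions, which lost it.

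**The concern.** Uptake and retention are different quantities. An early rise shows that the agent arrived. Retention concerns what is still there later. A single pre/post change can speak to retention only if the post-injection scan is late, and the plan does not say that it is.

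On the protocol's own account, an immediate rise is expected in any vascular tissue, with or without the transporter. A significant test on that scan would follow section 7.3.1 to the letter and leave the retention half of the objective unanswered. No other planned analysis covers it. The MRI signal change that section 7.3.2 correlates with OATP1B3 expression has no time point either, so the comparison closest to the biomarker question has the same gap. The study is open-label, and nothing in the plan prevents the scan from being chosen once the images have been seen.

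**Working it through.** **1. Where a time point could be named.**

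| Section | What it fixes | Scan named? |
|---|---|---|
| 7.3.1 | paired t-test or Wilcoxon on log values | no |
| 3.5.1 (cited by 7.3.1) | formula for the enhancement ratio | no |
| 7.4 | SD, fold change, power, lesion averaging | no |
| 7.3.2 | correlation of signal change with expression | no |
| 3.1.1 | ratios at all four time points | all, none primary |
| 1.2.4 | persistence versus washout | 20 minutes, as background only |

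**2. The plan's own power figure.** Inputs from section 7.4: SD of the log signal ratio 0.25, n = 10, 5% level, 1.2-fold change, stated power 83%. For a paired t-test the noncentrality is log(fold)/SD × √n, with n − 1 degrees of freedom.
- Log base 2: 0.263/0.25 × √10 = 3.33, two-sided power 84.1%. This is close to the stated 83%.
- Natural log: 0.182/0.25 × √10 = 2.31, two-sided power 53.9%.

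The stated figure is therefore near the log2 result, and it is the power of one test at one unnamed scan.

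**3. How small a change is significant.** The smallest significant mean log change is t(0.975, n − 1) × 0.25/√n. For n = 10 this is 2.262 × 0.25/3.162 = 0.179, which is 1.13-fold on the log2 scale or 1.20-fold on the natural-log scale. For n = 15 (the advanced arm in section 7.1; section 3.1 says 10) it is 0.138, which is 1.10-fold or 1.15-fold. If the SD of 0.25 holds, a modest early vascular rise would be enough.

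**4. If every scan is tested at 5%.** With no true change at any scan and independent tests, the chance of at least one significant result is 1 − 0.95^4 = 18.5% per arm. The four log ratios share one pre-injection value, so positive correlation is likely. The documents give none. Simulating four equally correlated paired t-tests gives:

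| Assumed correlation | At least one false positive, n = 10 or 15 |
|---|---|
| 0.5 | about 16% |
| 0.7 | about 14% |
| 0.9 | about 10% |

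Bonferroni over four scans (0.05/4 = 0.0125 each) would cut the power for a 1.2-fold change, on the log2 scale, from 84.1% to 60.0% at n = 10 and from 96.6% to 86.7% at n = 15. One pre-specified scan leaves the planned power as it is, provided the SD of 0.25 applies to that scan.

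**5. Whether an early-to-late contrast can describe retention.** Write E = (S_post − S_pre)/S_pre, the section 3.5.1 ratio as applied to signal intensity. Three illustrative lesions:

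| S_imm/S_pre | S_20/S_pre | E_imm | E_20 | E_20 − E_imm |
|---|---|---|---|---|
| 1.0 | 1.0 | 0 | 0 | 0 |
| 1.2 | 1.0 | 0.2 | 0 | −0.2 |
| 3.0 | 2.0 | 2.0 | 1.0 | −1.0 |

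The first lesion never enhanced, yet shows no loss. The third still enhances strongly, yet shows the largest loss. The difference is informative only when read with the early enhancement and the late level.

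**6. Precision of that contrast.** The documents give no SD for it. The 95% CI half-width is t(0.975, n − 1) × SD/√n. For assumed SDs of 0.15, 0.25 and 0.35 it is 0.11, 0.18 and 0.25 at n = 10, and 0.08, 0.14 and 0.19 at n = 15.

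**The case against.** The best defence is that this is an open-label pilot with no success rule or go/no-go decision tied to the p-value, and that section 3.1.1 computes ratios at every time point. Comparing every scan with baseline is then at least as natural a reading as picking one, and the early-to-late pattern would be visible. Section 7.4 also expects a smaller change where OATP1B3 expression is lower, which treats the tested change as transporter-related. All of this is fair, and it makes it less likely that an immediate rise would be presented as retention. It does not close the gap: on the all-scans reading there is no multiplicity rule, no scan decides the primary result, and still no analysis contrasts early with late.

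A reader might go further and infer that the same patients would give opposite primary results depending on the scan. For example, an arm that rises 1.5-fold immediately and is back at baseline by 20 minutes would be significant 99.5% of the time (n = 10, natural log) on the first scan and 5% on the second. The documents do not support this as a forecast. It is power under one assumed change set beside the 5% level under another. No early or late enhancement size is given for prostate lesions, and the SD of 0.25 comes from liver cancer patients at an unstated scan time.

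Nor does naming the 20-minute scan settle everything. That time follows the rationale's liver-tumour discussion, is not shown to be best in prostate lesions, and may still capture incomplete washout.

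**Conclusion.** The concern holds as a gap in specification and should be fixed. The primary analysis assigns two quantities to one pre/post test, leaves open which of four scans it uses, and includes no analysis of retention. This rests on the text alone and needs no numerical assumption.

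Of the figures, 18.5% is exact for four independent tests, while the range of about 10% to 16% depends on assumed correlations. Both describe the case of no change at any scan. They measure the cost of an undefined family of tests, not the probability that early enhancement is misread as retention, which the documents do not allow anyone to estimate. The documents also do not show that the investigators intend to report the immediate scan as retention; they show only that the plan would permit it.

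**What to change.** In section 7.3.1, for each arm:

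1. Pre-specify one late scan for the primary paired test of log(S_post/S_pre), where S is the signal intensity in the volume of interest. The 20-minute scan is the choice that section 1.2.4 supports. Report 60 minutes as a further late measure, and the immediate and 10-minute scans as a supportive time course. If all four scans are kept as primary, state the multiplicity adjustment and its effect on power.
2. Assess retention by the paired early-to-late change in the section 3.5.1 enhancement ratio, with a 95% CI, read together with the size of the early enhancement and the late level.
3. State that an immediate change alone is not evidence of retention, and that a late change may still include incomplete washout.

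In section 7.3.2, use the same late-scan quantity as the MRI signal change that is correlated with OATP1B3 expression.

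Section 3.6.1.3 makes an adverse event assessment 15 minutes after injection a condition for scans due immediately and at about 10 minutes. These statements must be reconciled so that the early scans are well defined. Which timing is right is for the investigators to decide.

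The cost is wording, with no added scans or patients, and it should be done before the images are analysed. The downsides are that one time point is placed above the others on evidence from outside prostate lesions, and that the precision of the retention contrast is unknown until its SD has been observed.

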#### **7.3.2 Secondary Efficacy Analysis**

The secondary objective of the study is to evaluate Eovist® MR parameters with respect to OATP1B3 lesion expression.

Imaging will be performed on 2 subgroups of prostate cancer patients. Subgroup 1 consists of early stage (non-metastatic) patients, subgroup 2 late stage (confirmed metastatic with prior hormonal ablation therapy) patients. It is expected that OATP1B3 expression is higher in late stage patients (subgroup 2) than in early stage patients.

For patients in subgroup 2, expression of OATP1B3 will be determined in soft tissue or bone lesions taken from biopsy and will be correlated with MRI signal change by both Pearson and Spearman correlation coefficient.

As OATP1B3 SNPs also alter androgen uptake, affecting outcome of androgen deprivation therapy (ADT) [3, 4], genotype will also be compared to progression-free survival on ADT. Genotypes will be compared to these endpoints using the chi-squared and/or Fisher's exact test, or the log-rank test as appropriate.

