#### 1.1.3 Exploratory Objective

- Evaluate MR contrast enhancement parameters with respect to OATP1B3 expression.

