### 3 STUDY IMPLEMENTATION

#### 3.1 Study Design

This is an open-label, single-center pilot study. Twenty evaluable subjects will be enrolled, 10 subjects with localized prostate cancer and 10 subjects with advanced prostate cancer with soft tissue or bone involvement. A subject is considered evaluable if he completes pre and post Eovist® injection MRI scans and has sufficient tissue for OATP1B3 IHC.

- Localized disease:
  - If existing pathologic tissue can be linked with confidence to an MRI-defined lesion (i.e. pathologic specimen is labeled as to location) then that tissue can be used for OATP1B3 expression.
  - Otherwise the tissue obtained during image guided biopsy at NCI will be used for OATP1B3 expression testing.
  - Prostatectomy specimens may be a source of tissue if the above sources are not available and the patient undergoes prostatectomy.
- Advanced disease:
  - If clinically acquired tissue is not available, the patient must be willing to have a percutaneous needle biopsy of a soft tissue lesion or metastatic bone lesion (measuring  $\geq 1.5\text{cm}$  in diameter at CT or MRI scan).

All tissue samples (either biopsy specimens from localized intraprostatic lesions or prostatectomy specimens in the localized disease arm or biopsy specimens from the soft tissue or metastatic bone lesions in the advanced disease arm) for immunohistochemical (IHC) analysis must be acquired within  $\pm 20$  weeks (assuming no intervening therapy) of Eovist® imaging.

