#### **3.1.4 Immunohistochemistry**

Immunohistochemistry analysis will include exploratory assessment of OATP1B3 expression. Analyses will be performed on tumor from all specimens obtained and, will be performed at NIH. The [name] Lab has previously published immunofluorescence methods to detect OATP1B3 in prostate tissue sections isolated from men with benign prostatic hyperplasia, and prostate cancer [3]. The assay was able to distinguish between expressing and non-expressing tumors using a primary OATP1B3 antibody purchased from Santa Cruz Biotech. This will be used for IHC analysis. Moreover, we are currently developing better methods of detection in collaboration with [name] (University of Colorado Denver). We are also collaborating with [name] (University of Kentucky) who has recently published IHC methods using antibodies developed in-house. This is a topic which is still under investigation. The scope of collaboration with these groups will be limited to data exchange, but will not include sending out tissue samples.

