#### **3.5.3 Histological Correlations**

OATP1B3 expression will be confirmed by staining for OATP1B3 in tissue samples on an investigational basis. IHC analysis will be conducted by one NCI pathologist and will be based on grade of positivity (0 (no staining), 1 (weak staining), 2 (moderate staining) or 3 (strong staining)).

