### 3.6 Study Calendar

The timing of study events in the following descriptions is relative to the administration of EOVIST®.

Procedure	Screening a	Baseline b	MR imaging			Scheduled Post-MRI c
			Just prior to MRI	Pre-injection MRI scan	Post injection MRI scan	
Informed consent	X					
Study entry criteria	X					
Demographic information	X					
Medical history and concurrent diseases	X					
Prior/concomitant medications	X					
Injection site monitoring				X	X d	X
Vital signs	X	X			X e	
Acute Care Panel, Hepatic Panel, Mineral Panel, PSA, & CBC	X f					
OATP1B3 Genotype analysis	X g					
Biopsy specimen available for OATP1B3 expression	X h, i					
Intravenous line started			X			
Eovist® injection				X		
Adverse Event Monitoring			X	X	X	X
MR Imaging				X	X j	
Biopsy Procedure						X k, l
Prostatectomy						X m
OATP expression and Comparative Analyses						X

a: Within 21 days of administrations of Eovist®

b: The day of MR imaging until just prior to administration of Eovist ®

- c. Timing of events is relative to administration of Eovist®
- d: 5 minutes post-Eovist® injection
- e: At the end of all scanning
- f: Clinical blood sample assessments must be performed within 21 days prior to administration of Eovist®.
- g: Will be performed at [name] Lab.
- h: For the localized disease arm, existing pathologic tissue (obtained <20 weeks before Eovist MRI) will be screened to see if it can be linked to MRI visible lesion in the patient candidate for Eovist MRI. Otherwise the tissue obtained from image guided biopsy (standard of care) at NCI will be used for OATP1B3 expression.
- i: For the advanced disease arm, availability of the previously (<20 weeks) obtained clinically acquired tissue will be checked.
- j: Immediately, 10, 20, & 60 minutes post-Eovist® injection
- k: To be conducted within <20 weeks after Eovist® enhanced MRI
- l: This applies for the advanced disease arm and will be conducted from a soft tissue or metastatic bone lesion (measuring  $\geq 1.5\text{cm}$  in diameter).
- m: This applies for the localized disease arm and will serve as a source of tissue only if previously acquired biopsy (confidently linked to an MRI visible lesion) or image guided standard of care biopsy at NCI will not be available.

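### Section 7.3.2 plans the OATP1B3-versus-MRI correlation for the advanced arm only, and Section 7 gives no analysis of localized-arm IHC, although the objective and the evaluability rule cover both arms

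*Combined protocol and SAP*

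**What the plan says.** Section 7.3.2 opens with an aim that has no arm limit, describes both subgroups, and expects higher expression in late-stage disease. It then gives its one expression-imaging method, Pearson and Spearman correlation with MRI signal change, for the advanced arm: "For patients in subgroup 2, expression of OATP1B3 will be determined in soft tissue or bone lesions taken from biopsy". Subgroup 1 gets no test, estimate or summary of expression.

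Other sections treat the question as belonging to both arms:

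- Objective 1.1.3: "Evaluate MR contrast enhancement parameters with respect to OATP1B3 expression", with no stage named.
- Rationale, 1.2.4: "Eovist® will be used in patients with localized and metastatic prostate cancer in order to determine if this method is feasible". The same sentence goes on to ask about correlation with OATP1B3 expression.
- Section 3.1: a subject in either arm is evaluable if he "completes pre and post Eovist® injection MRI scans and has sufficient tissue for OATP1B3 IHC".
- Section 3.1, localized disease: "If existing pathologic tissue can be linked with confidence to an MRI-defined lesion", that tissue may be used for expression.
- Section 3.1.4: "Analyses will be performed on tumor from all specimens obtained".
- Study Calendar, 3.6: a row reads "OATP expression and Comparative Analyses", with no arm and no method.

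**The concern.** Whether Eovist uptake tracks OATP1B3 expression is the biomarker question that motivates the study. The plan makes IHC tissue a condition of evaluability for localized subjects and stains it, but never says how the result will be set against their imaging. An analyst following Section 7 would report the correlation in advanced disease and nothing for localized disease. Any later use of the localized data would then be an unplanned choice made after seeing the results.

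**Working it through.** **Text check.** What each part of Section 7 does with localized-arm IHC:

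| Section | Content | Uses localized IHC? |
|---|---|---|
| 7.1, 7.2 | Accrual, demographics | No |
| 7.3.1 | Pre/post MRI change | No |
| 7.3.2 | Expression-MRI correlation, subgroup 2; genotype against progression-free survival on ADT | No |
| 7.4 | Power for pre/post MRI change | No |

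Section 3.5.3 defines a 0-3 staining grade but no analysis. The plan states no sample size or power for the correlation, so there is no figure of its own to reproduce.

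**Numbers of subjects.** The Precis and 7.1 give 10 localized + 15 advanced = 25. Section 3.1 gives 10 + 10 = 20. The planned correlation therefore has 15 (or 10) subjects, against at most 25 (or 20).

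**Precision at an assumed r = 0.5.** Fisher z, approximate for Spearman: CI = tanh(atanh(r) ± 1.96/√(n-3-k)), with k = 1 when an arm term is fitted and atanh(0.5) = 0.549.

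- n=15: 0.549 ± 1.96/√12 gives -0.02 to 0.81.
- n=25, arm term: 0.549 ± 1.96/√21 gives 0.12 to 0.75.
- n=10: 0.549 ± 1.96/√7 gives -0.19 to 0.86.
- n=20, arm term: 0.549 ± 1.96/√16 gives 0.06 to 0.78.

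Correlation detectable with 80% power (two-sided 5%, assumed), tanh((1.96+0.84)/√(n-3-k)): 0.67 at n=15, 0.55 at n=25 with arm term, 0.79 at n=10.

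**Why r need not stay at 0.5.** Assume a common slope and equal residual variance. Take the Precis background rates (92% of metastases, 52% of localized lesions express OATP1B3) as the share above grade 0, which the documents do not establish. Suppose advanced positives are spread evenly over grades 1-3:

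- Advanced grade variance = 0.92 × 14/3 - (0.92 × 2)² = 0.908.
- Localized variance if all positives are grade 1 = 0.52 × 0.48 = 0.250.
- Pooled within-arm variance = (15 × 0.908 + 10 × 0.250)/25 = 0.645.
- If r = 0.5 in the advanced arm, residual variance in slope units = 3 × 0.908 = 2.724.
- Pooled r = √(0.645/(0.645 + 2.724)) ≈ 0.44, with CI 0.04 to 0.72 at n=25 with arm term.

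**Range of information gain.** Gain = 1 + (10 × V_L/ρ²)/(15 × V_A), where V_L and V_A are the localized and advanced grade variances and ρ is the localized/advanced ratio of residual SDs. With V_A = 0.908, 15 × V_A = 13.62.

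- Localized positives also spread evenly (V_L = 0.52 × 14/3 - (0.52 × 2)² = 1.345), ρ=1: 1 + 13.45/13.62 = 1.99.
- Localized positives all grade 1, ρ=1: 1 + 2.50/13.62 = 1.18.
- 90% of localized lesions stain, all grade 1 (V_L = 0.09), ρ=1: 1 + 0.90/13.62 = 1.07.
- Localized positives all grade 1, ρ=2: 1 + (2.50/4)/13.62 = 1.05.
- All positives share one grade in both arms (V_A = 0.92 × 0.08 = 0.0736), ρ=1: 1 + 2.496/1.104 = 3.26.

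The gain therefore runs from about 1.05-fold to about 3-fold, depending on quantities that the documents do not give.

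**The case against.** The strongest reply is that both arms were probably intended: the opening sentence of 7.3.2 is unrestricted, and the calendar row limits nothing. That intent is plausible. But the opening sentence states an aim, the calendar row supplies no method, and the only method given is confined to subgroup 2. The text needs correcting on either reading.

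A second reply is that lower expected expression in localized disease justifies leaving it out. The plan does not say so, and a correlation needs variation in expression. If the background rates do translate to grade 0 versus positive, one would expect 10 × 0.48 = 4.8 negative lesions in the localized arm against 15 × 0.08 = 1.2 in the advanced arm. The chance of no negatives among 15 advanced subjects would be 0.92^15 = 29%.

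Three objections limit the point and stand:

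- A reader might infer that lesion-matched imaging and tissue are already required from all 25 subjects. Section 3.1 requires only completed scans and enough tissue. Its linking condition covers existing localized tissue, and neither 3.1 nor calendar note m states a linking step for prostatectomy specimens.
- A reader might infer that a definite share of the information is being discarded. The range above is too wide for any single percentage.
- The pooled estimate assumes a common slope across arms that differ in stage, lesion site and possibly coil. Section 3.1.1 leaves the endorectal coil optional, while 3.6.1.3 calls for it in the localized arm.

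**Conclusion.** The gap in the text is clear: the specified correlation excludes the localized arm, and Section 7 analyses that arm's IHC nowhere. As written, the plan gives no answer on this question for localized disease and uses 15 (or 10) of up to 25 (or 20) subjects, with the localized contribution possibly below 10.

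Confidence is high for the text only. The intervals assume a true correlation, and the gain rests on assumed grade spreads and residual variances. The localized estimate alone, at n=10, can only be descriptive.

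The weight is modest. Section 1.1.3 makes this an exploratory objective of a pilot study. The documents do not support reading the gap as a flaw in the primary analysis or the sample size, since both rest on the pre/post signal change. The change is still worth making, because it is cheap and settles the handling of localized data in advance.

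**What to change.** In Section 7.3.2:

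- Extend the correlation to both arms. Use the signal change of the lesion that supplied the tissue: the biopsied lesion, or the MRI-defined lesion to which biopsy or prostatectomy tissue can be linked. The multi-lesion averaging in 7.4 is stated for the paired t-test and should not be carried over.
- Report how many subjects in each arm have tissue that cannot be linked to an imaged lesion.
- Give a descriptive Spearman coefficient within each arm, plus one arm-adjusted estimate: partial Spearman, or regression of log signal ratio on the 0-3 grade with an arm term. State the common-slope assumption beside the pooled result.
- Label the analysis exploratory, as in 1.1.3. Section 7.3.2 currently calls it secondary.

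The cost is a few lines of plan text and analysis code, with no new subjects and no added biopsy or scan. Recording the link between prostatectomy tissue and the MRI lesion may be a small extra step, since no current section states it.
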